8.1. Immunogenicity Assessments

No generally accepted immunological correlate of protection has been demonstrated for SARS-CoV-2 to date. If a correlate or threshold for protection against COVID-19 is established in terms of humoral immunity, then a statistical comparison to that correlate or threshold will substitute NI testing to immune responses to vaccine at release, as outlined in the study statistical analytical plan (SAP).

Venous blood samples will be collected for assessment of humoral immune responses. Sample volumes and time points are detailed in the [Schedule of Activities](#) in Section 1.3.

If the participant is unable to complete the study but they did not withdraw consent, immunogenicity samples will be taken at the early exit visit, but only if the early exit visit is at least 10 days after the previous immunology blood draw. See the [Schedule of Activities](#) for further details.

Humoral immunogenicity assays may include, but are not limited to, the assays summarized in [Table 4](#).

Table 4: Summary of Humoral Immunogenicity Assays

Assay	Purpose
Humoral Immunogenicity	
Primary endpoints	
HI assay ^a	Analysis of HI to influenza strains
SARS-CoV-2 binding antibodies (ELISA)	Analysis of antibodies binding to SARS-CoV-2 or individual SARS-CoV-2 proteins (eg, S protein)
Secondary endpoints	
HI assay ^a	Analysis of HI to influenza strains
SARS-CoV-2 binding antibodies (ELISA)	Analysis of antibodies binding to SARS-CoV-2 or individual SARS-CoV-2 proteins (eg, S protein)
Exploratory endpoints	
HI assay	Analysis of HI to influenza strains

SARS-CoV-2 binding antibodies (ELISA)	Analysis of antibodies binding to SARS-CoV-2 or individual SARS-CoV-2 proteins (eg, S protein)
SARS-CoV-2 neutralization (VNA)	Analysis of neutralizing antibodies to the wild-type virus and/or pseudovirion expressing S protein
Adenovirus neutralization	Adenovirus 26 neutralization assay to evaluate neutralizing antibody responses against the Ad26 vector
SARS-CoV-2 binding antibodies (ELISA and/or SARS-CoV-2 immunoglobulin assay)	Analysis of antibodies binding to the SARS-CoV-2 N protein
Functional and molecular antibody characterization	Analysis of antibody characteristics including Fc-mediated viral clearance, avidity, Fc characteristics, Ig subclass and IgG isotype

ELISA = enzyme-linked immunosorbent assay; Fc = fragment crystallizable; HI assay = Hemagglutination inhibition (HI) assay; Ig = immunoglobulin; S = Spike; SARS-CoV2 = severe acute respiratory syndrome coronavirus-2; VNA = virus neutralization assay.

a. The HI antibody titers against influenza virus strains recommended by the World Health Organization (WHO) for use in 2021-2022 in the Northern Hemisphere season will be measured using a validated HI assay platform.

8.2. Safety Assessments

Adverse events will be reported and followed by the investigator as specified in Section [8.3](#) and Appendix 4 (Section [10.4](#)).

Any clinically relevant changes occurring during the study period must be recorded on the AE section of the eCRF.

Any clinically significant abnormalities will be followed by the investigator until resolution or until a clinically stable condition is reached. For those abnormalities persisting at the end of the study/early withdrawal, the outcome should be documented in the participant's medical chart.

The study will include the following evaluations of safety and tolerability according to the time points provided in the [Schedule of Activities](#).

8.2.1. Physical Examinations

A full physical examination, including height and body weight, will be carried out at screening.

At all other visits, an abbreviated, symptom-directed examination might be performed by the investigator based on any clinically relevant issues or symptoms, and medical history. Symptom-directed physical examination may be repeated if deemed necessary by the investigator.

Physical examinations will be performed by the investigator or designated medically trained clinician. Any clinically relevant abnormalities or changes in severity observed during the review of body systems should be documented in the eCRF.

8.2.2. Vital Signs

Body temperature (oral route preferred, or in accordance with the local standard of care), pulse/heart rate, respiratory rate, and blood pressure will be assessed.

Participants will utilize a diary to record body temperature measurements post-vaccination (see Section [8](#)).

Blood pressure and pulse/heart rate measurements will be assessed preferably supine with a completely automated device. Manual techniques will be used only if an automated device is not available.

Blood pressure and pulse/heart rate measurements should be preceded by at least 5 minutes of rest in a quiet setting without distractions (eg, television, cell phones). Vital sign measurements are recommended before blood sampling.

8.2.3. Clinical Safety Laboratory Assessments

Blood samples for clinical laboratory assessments (as detailed in Section 10.2, Appendix 2) will be collected as described in the Schedule of Activities in Section 1.3.

In case of a thrombotic event, thrombocytopenia, or TTS occurring post-vaccination, every effort should be made to collect in a local hospital/laboratory the blood test results obtained to ensure that the treating physician performs a rapid diagnosis and treatment.

This information should be reported through the TTS AESI form (see Section 10.8, Appendix 8) electronically per instructions in the eCRF completion guidelines. In addition, every effort should be made to collect blood samples from the participant for a platelet count (local laboratory or substitute for local laboratory) and other applicable testing (central laboratory; eg, anti-PF4 see the Schedule of Activities in Section 1.3.2 and Section 10.2, Appendix 2).

The investigator will review the laboratory test results performed locally and investigate potential cases of thrombosis (per Appendix 9, Section 10.9) to assist the investigation of the AESI, and document it in eDC.

See Section 8.3.6.1 for details on laboratory tests to be reported for post-vaccination thrombocytopenia.

8.2.4. Pregnancy Testing

A urine pregnancy test for participants of childbearing potential will be performed at screening and before each vaccination.

Additional pregnancy tests may be performed for participants of childbearing potential, as determined necessary by the investigator or required by local regulation, to establish the absence of pregnancy at any time during the participation in the study.

8.3. Adverse Events, Serious Adverse Events, Medically-attended Adverse Events, Adverse Events of Special Interest, and Other Safety Reporting

Timely, accurate, and complete reporting and analysis of safety information, including AEs, SAEs, MAAEs, AESIs, and PQCs, from clinical studies are crucial for the protection of participants, investigators, and the sponsor, and are mandated by regulatory agencies worldwide.

The sponsor has established Standard Operating Procedures in conformity with regulatory requirements worldwide to ensure appropriate reporting of safety information; all clinical studies conducted by the sponsor or its affiliates will be conducted in accordance with those procedures.

Adverse events will be reported by the participant (or, when appropriate, by a caregiver, surrogate, or the participant's legally acceptable representative) for the duration of the study.

Further details on AEs, SAEs, MAAEs, AESIs, and PQCs can be found in Section [10.4, Appendix 4](#).

8.3.1. Time Period and Frequency for Collecting Adverse Event, Medically-attended Adverse Event, Adverse Event of Special Interest, and Serious Adverse Event Information

All Adverse Events

Adverse events and special reporting situations, whether serious or non-serious, that are related to study procedures or that are related to non-investigational sponsor products will be reported from the time a signed and dated ICF is obtained until the end of the study/early withdrawal.

Clinically relevant medical events not meeting the above criteria and occurring between signing of ICF and moment of first vaccination will be collected on the Medical History eCRF page as pre-existing conditions.

Solicited AEs, collected through a diary, will be recorded for each vaccination from the time of vaccination until 7 days post-vaccination (or until resolution).

All unsolicited AEs and special reporting situations, whether serious or non-serious, will be reported for each vaccination from the time of vaccination until 28 days post-vaccination. Unsolicited adverse events with the onset date outside the timeframe defined above (>28 days after each study vaccination), which are ongoing on the day of the subsequent vaccination, should be recorded as such.

At each visit the participant will be asked if they have had a private/off-study COVID-19 test. If a participant receives a positive SARS-CoV-2 result from a private/off-study test during the study period (whether through PCR or serological testing) the event should be reported as an AE or as an SAE if the event meets the criteria of an SAE. The participant can continue in the study in accordance with local country and site level recommendations for COVID-19. Any positive SARS-CoV-2 result should be recorded in the eCRF. Previous SARS-CoV-2 infection should be documented as medical history and does not preclude participation in the study.

All SAEs, AESIs, and AEs leading to discontinuation from the study/vaccination (regardless of the causal relationship) are to be reported from the moment of first vaccination until the end of the study, which may include contact for safety follow-up. The sponsor will evaluate any safety information that is spontaneously reported by an investigator beyond the time frame specified in the protocol.

MAAEs are defined as AEs with medically-attended visits including hospital, emergency room, urgent care clinic, or other visits to or from medical personnel for any reason. Routine medical visits for chronic comorbidities (or study visits) will not be considered medically-attended visits. New onset of chronic diseases will be collected as part of the MAAEs. MAAEs are to be reported for all participants throughout the study.

As long as the participant remains in the study, all AEs will be followed until resolved, until clinically stable or the end of the study, as applicable. The investigator's assessment of ongoing AEs at the time of each participant's last visit should be documented in the participant's medical chart.

Adverse Events of Special Interest

TTs is considered to be an AESI. Suspected AESIs (thrombotic events and thrombocytopenia [defined as platelet count below 150,000/ μ L ([Brighton Collaboration 2021](#))] post-vaccination) will be recorded from the moment of vaccination until the end of the study/early withdrawal. An AESI Adjudication Committee with appropriate expertise will be established to evaluate each suspected AESI and determine whether it is a case of TTs (see Section [8.3.6](#)).

All AESIs occurring during the study period must be reported to the sponsor by study site personnel within 24 hours of their knowledge of the event and complete the procedures indicated in the Schedule of Activities in Section [1.3.2](#).

Serious Adverse Events

All SAEs, as well as PQCs, occurring during the study must be reported to the appropriate sponsor contact person by study site personnel within 24 hours of their knowledge of the event.

Serious adverse events, including those spontaneously reported to the investigator, must be reported using an SAE form. The sponsor will evaluate any safety information that is spontaneously reported by an investigator beyond the time frame specified in the protocol.

Information regarding SAEs will be transmitted to the sponsor using the SAE Form and Safety Report Form of the CRF, which must be completed and reviewed by a physician from the study site, and transmitted to the sponsor within 24 hours. The initial and follow-up reports of an SAE should be transmitted electronically or by facsimile (fax). Telephone reporting should be the exception and the reporter should be asked to complete the appropriate form(s) first.

8.3.2. Method of Detecting Adverse Events, Medically-attended Adverse Events, Adverse Events of Special Interest, and Serious Adverse Events

Care will be taken not to introduce bias when detecting AEs, MAAEs, suspected AESIs, or SAEs. Open-ended and nonleading verbal questioning of the participant is the preferred method to inquire about AE occurrence.

Solicited Adverse Events

Solicited AEs are used to assess the reactogenicity of the study vaccine and are predefined local (at injection site) and systemic events for which the participant is specifically questioned and which are noted by participants in their diary.

After each vaccination, participants will remain under observation at the study site for at least 15 minutes for presence of any acute reactions and solicited events.

In addition, participants will record solicited signs and symptoms in a diary for 7 days post-vaccination (or until resolution). All participants will be provided with a diary and instructions on how to complete the diary (see Overview in Section [8](#)).

Electronic diary information will be transferred from the e-diary source to the sponsor. After review and verbal discussion of the initial electronic diary entries with the participant, the investigator will complete his/her own assessment in the relevant sections of the CRF (ie, investigator's assessment of reactogenicity). Once a solicited symptom from a diary is verified and considered to be of severity Grade 1 or above, it will be recorded as a solicited adverse event per FDA toxicity grading (See Appendix 6, Section [10.6](#)).

Solicited Injection Site (Local) Adverse Events

Participants will be asked to note in the diary occurrences of local reaction at the injection site namely pain/tenderness, erythema, swelling, and systemic reactions, namely fatigue, headache, nausea, and myalgia daily for 7 days post-vaccination (or until resolution, whatever happens first). The extent (largest diameter) of any erythema and swelling should be measured (using the ruler supplied) and recorded daily. The case definitions for solicited injection site events can be found in the references ([Gidudu 2012](#); [Kohl 2007](#)).

Solicited Systemic Adverse Events

Participants will be instructed on how to record daily temperature using a thermometer for home use. Participants should record the temperature in the diary starting in the evening of the day of vaccination, and then daily for the next 7 days approximately at the same time each day. If more than one measurement is made on any given day, the highest temperature of that day should be recorded.

Fever is defined as endogenous elevation of body temperature $\geq 38^{\circ}\text{C}$ (100.4°F). (See Appendix 6, Section [10.6](#).)

Unsolicited Adverse Events

Unsolicited AEs are all AEs for which the participant is not specifically questioned in the participant diary.

Medically-attended Adverse Events

MAAEs are AEs with medically-attended visits including hospital, emergency room, urgent care clinic, or other visits to or from medical personnel for any reason. New onset of chronic diseases

will be collected as part of the MAAEs. Routine study visits will not be considered medically-attended visits.

Adverse Events of Special Interest

For details about AESIs, refer to Section [8.3.6](#).

8.3.3. Follow-up of Adverse Events, Medically-attended Adverse Events, Adverse Events of Special Interest, and Serious Adverse Events

The investigator is obligated to perform or arrange for the conduct of supplemental measurements and evaluations as medically indicated to elucidate the nature and causality of the AE, MAAE, AESI, SAE, or PQC as fully as possible. This may include additional laboratory tests or investigations, histopathological examinations, or consultation with other health care professionals.

Adverse events, including pregnancy, will be followed by the investigator as specified in Section [10.4, Appendix 4](#).

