a. The HI antibody titers against influenza virus strains recommended by the World Health Organization (WHO) for use in 2021-2022 in the Northern Hemisphere season will be measured using a validated HI assay platform.

SAFETY EVALUATIONS

After each vaccination, participants will remain under observation at the study site for at least 15 minutes for presence of any acute reactions and solicited events. Participants will be asked to note in the diary occurrences of local reactions at injection site namely pain/tenderness, erythema, swelling, and systemic reactions namely fatigue, headache, nausea, and myalgia daily for 7 days post-vaccination (or until resolution).

Participants will be instructed on how to record daily temperature and local reactions using a thermometer and a ruler provided for home use. Participants should record the temperature in the diary starting in the evening of the day of vaccination, and then daily for the next 7 days approximately at the same time each day. If more than one measurement is made on any given day, the highest temperature of that day should be recorded.

Adverse events and special reporting situations, whether serious or non-serious, that are related to study procedures or that are related to non-investigational sponsor products will be reported from the time a signed and dated informed consent form (ICF) is obtained until the end of the study/early withdrawal.

Thrombosis with thrombocytopenia syndrome is considered to be an adverse event of special interest (AESI). Suspected AESIs (thrombotic events and thrombocytopenia [defined as platelet count below 150,000/ μ L]) will be monitored from the moment of vaccination until the end of the study/early withdrawal. An AESI Adjudication Committee with appropriate expertise will be established to evaluate each suspected AESI and determine whether it is a case of thrombosis with thrombocytopenia syndrome (TTS).

All unsolicited AEs will be reported for each vaccination from the time of vaccination until 28 days post-vaccination. All SAEs, AESIs, and AEs leading to discontinuation from the study/vaccination (regardless of the causal relationship) are to be reported from the moment of first vaccination until the end of the study. The investigator's assessment of ongoing AEs at the time of each participant's last visit should be documented in the participant's medical chart.

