- o. Suspected AESIs are to be reported from the moment of vaccination until the end of the study (see Section 8.3.1).
- p. At each visit the participant will be asked if they have had a private/off study COVID 19 test. If a participant receives a positive SARS CoV 2 result from a private/off study test (whether through PCR or serological testing) the event should be reported as medical history, AE or SAE if the event meets the criteria for an SAE. The participant can continue in the study in accordance with country and site level recommendations for COVID 19.
- q. MAAEs are to be reported throughout the study. New onset of chronic diseases will be collected as part of the MAAEs.
- r. Concomitant therapies such as analgesic/antipyretic medications and non steroidal anti inflammatory drugs, corticosteroids, antihistamines, and vaccinations must be recorded (including dose and frequency) from the first dose of study vaccine until 28 days after administration of the last study vaccine. (See protocol Section 6.8 for collection and recording of concomitant therapies associated with SAEs, solicited and unsolicited AEs, suspected AESIs, and MAAEs. All other concomitant therapies should be recorded if administered in conjunction with new or worsening AEs reported per protocol requirements outlined in Section 8.3.1).
- s. On Day 1, the participant's diary, a ruler, and a thermometer will be distributed to each participant. On Day 29, the site is to conduct the last vaccination visit and confirm any missing solicited safety data points.
- t. The reactogenicity vaccination folder should be completed and local and systemic symptoms should be verified and entered in eDC. If a solicited event is still ongoing 7 days after vaccination, the participant should continue reporting symptoms until resolution. If symptoms continue beyond Day 7, the diary should be reviewed again at the next visit.

AE adverse event; AESI adverse event of special interest; COVID 19 coronavirus disease 2019; d day(s); eCRF electronic case report form; ICF informed consent form; MAAE medically attended adverse event; meds medication; mo months; N/A not applicable; PCR polymerase chain reaction; SAE serious adverse event; SARS CoV 2 severe acute respiratory syndrome coronavirus 2; vac vaccination; vp virus particles.

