### **5.6.1.2. Analysis of Adverse Events**

Safety analyses will be performed on the FAS. Continuous variables will be summarized using the following statistics, as appropriate: number of observations, median, minimum, and maximum. Frequencies and percentages (one decimal place) will be generated for categorical variables. No formal comparisons between groups will be provided.

Safety data will be analyzed and presented by study intervention and phase. Denominator for the percentages is the number of participants in the considered population and phase for a certain regimen (incidence per 100 participants/phase).

Number and percentage of participants with at least one particular AE (unsolicited/solicited) will be tabulated. Unsolicited AEs will be summarized by System Organ Class and Preferred Term. Solicited AEs will be summarized by class (administration site, systemic) and preferred term.

For solicited AEs, the following tables will be provided: summary, by worst severity grade, at least grade 3, related (systemic only), time to onset (in days) and duration (in days). Note: Duration is defined as number of days from the start of the event until resolution of the event. The time to first onset is defined as (date of first onset – reference date + 1). The reference date is the start date of the vaccination period.

A tabulation of the distribution of temperatures per half degree intervals will also be provided.

For unsolicited AEs, the following tables will be provided: summary table (including SAE, fatal outcome, discontinuation and AESI), all events, most frequent, at least grade 3, permanent stop of vaccine, related, SAE, related SAE, potential AESI and AESI.

Unsolicited non-serious adverse events collected outside the 28-day period following the vaccination will be presented through listings.

Listings and/or participant narratives will be provided as appropriate, for those participants with a fatal outcome, discontinue study vaccinations due to an AE, discontinue study due to an AE, or experienced a severe SAE, or an AESI event.

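### Protocol 8.3.2 ends diary recording at the earlier of 7 days and resolution, which contradicts Schedule footnote t and does not fit the SAP's definition of duration

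*Protocol*

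**What the plan says.** Protocol 8.3.2 sets the diary rule twice. Its opening text on solicited events says that "participants will record solicited signs and symptoms in a diary for 7 days post-vaccination (or until resolution"), with no order between the two limits. The paragraph on injection site events, which also lists the four systemic symptoms, adds an order: "daily for 7 days post-vaccination (or until resolution, whatever happens first").

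Footnote t of the Schedule of Activities (Protocol 1.3.1) is explicit about longer events: "If a solicited event is still ongoing 7 days after vaccination, the participant should continue reporting symptoms until resolution". It adds: "If symptoms continue beyond Day 7, the diary should be reviewed again at the next visit".

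The Synopsis ("daily for 7 days post-vaccination (or until resolution")) and 8.3.1 ("from the time of vaccination until 7 days post-vaccination (or until resolution")) give both limits without ranking them. So do 4.1 and, for therapies linked to solicited events, 6.8. Temperature has a separate rule in 8.3.2: it is taken on the evening of vaccination "and then daily for the next 7 days approximately at the same time each day".

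On the analysis side, Protocol 9.4.5 plans frequencies of solicited events by severity and duration. SAP 5.6.1.2 tabulates time to onset and duration and states: "Duration is defined as number of days from the start of the event until resolution of the event". SAP 5.6.1.1 takes the solicited-event tables from the investigator's assessment pages. SAP 5.6.1.4 treats a participant with no reported event as event-free.

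**The concern.** For an event still present 7 days after vaccination, 8.3.2 and footnote t give opposite instructions and a site cannot follow both. The unordered phrase used elsewhere does not settle which one governs.

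Two kinds of information are at stake. The first is the resolution date of reactions that outlast the 7 days, which the duration table needs. The second is what happens inside the window after an early resolution: if recording stops then, a symptom that returns is not seen, although the endpoint covers solicited events for 7 days after each vaccination. Protocol 2.1 says it is unknown whether co-administration influences the reactogenicity of Ad26.COV2.S, so complete description of these reactions is part of what the study is for. If sites follow different passages, their diary data will not be comparable.

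**Working it through.** The plan gives no figure to reproduce, and no calculation of size is possible. The check sets the rules side by side and tests them on assumed dates.

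**Rules for an event ongoing 7 days after vaccination**

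| Place | Instruction |
|---|---|
| Protocol 8.3.2, injection site paragraph | Stop (7 days comes first) |
| Protocol 1.3.1, footnote t | Continue to resolution; review the diary at the next visit |
| Protocol 8, Overview | Diary can be reviewed at the next visit if symptoms are ongoing |
| Synopsis, 4.1, 8.3.1, opening text of 8.3.2 | Both limits named, no order |
| SAP 5.6.1.2 | Duration runs to resolution, no cap |

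**Rules for an event that resolves before 7 days.** The 8.3.2 paragraph says stop at resolution. The endpoint wording asks for 7 days. The temperature rule runs a fixed 7 days, so fever is not exposed to early stopping.

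**Illustration (dates assumed).** The Schedule places vaccination 1 at Day 1 and the 7-day contact at Day 8.

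- *Late resolution.* Pain starts on Day 2 and resolves on Day 12. Start to resolution is 12 − 2 = 10 days. With the diary stopped at Day 8, 8 − 2 = 6 days are observed and the diary holds no resolution date.
- *Early resolution.* A first symptom resolves on Day 3. If recording then stops, Days 4 to 8 (8 − 3 = 5 days) lie inside the window but are unobserved. If the rule applies symptom by symptom, only a recurrence of that symptom can be lost. If the whole diary is closed, a new symptom can be lost too.

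**What the SAP does with the gaps.** Under 5.6.1.4 an event that was never recorded leaves the participant counted as having none, so any loss inside the window lowers the reported incidence. For a completely missing end date, SAP 5.6.1.3 imputes the analysis cut-off or the end of the last period for period allocation, and later treats that date as complete when combining events. The SAP does not say whether this imputed date can enter the solicited duration table.

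**What can repair them.** Under 8.3.2 the investigator completes an assessment after discussing the diary entries with the participant; Section 8 places this at the 7-day contact, which has a ±3 day window. Protocol 8.3.1 keeps AEs under follow-up until resolved, stable or study end. These routes may supply a later resolution date. They are less able to recover a symptom that was never entered.

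**The case against.** The strongest reply is that this is one stray phrase. The ordering words occur once; every other passage omits them, including one in the same section, and footnote t and Section 8 plainly expect diary review beyond the 7 days. The SAP tables rest on the investigator's assessment and not directly on the diary, and AEs are followed to resolution in any case. Protocol 2.3.1 reports that most Ad26.COV2.S reactions last 1-2 days, so few should run past the limit. The rule applies to all groups under blinding, and the SAP plans no formal group comparison of safety.

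Most of this stands, and it limits the consequence. A reader might infer from 8.3.2 that the SAP's duration cannot be obtained, or that every long event will be truncated. The documents do not support that, because there are other routes to a resolution date. A reader might also infer that symptoms starting later in the week will be missed. That requires the whole diary to stop when one symptom resolves, which is the less natural reading; the e-diary instructions are not in the documents, so it cannot be confirmed. Onset after the 7-day window is outside the solicited endpoint under any reading.

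The reply does not remove the contradiction. The phrase is operative text in the section that defines how solicited events are detected, and diary instructions or training may draw on it. Short typical durations also work in the other direction: they make early resolution common, and that is where the literal rule could end recording inside the window.

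**Conclusion.** The point holds as an inconsistency with a possible, not a demonstrated, effect on the data. Read literally, 8.3.2 contradicts footnote t for any event ongoing at 7 days and does not supply what the SAP's duration definition needs. Where 8.3.2 is followed, resolution dates after the 7 days may be lost, and recurrences within the window (new symptoms only under the whole-diary reading) may go unrecorded and be counted as absent.

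The size is unknown: it depends on how many sites or diary screens follow 8.3.2 and on how many reactions outlast 7 days or recur. The effect is confined to descriptive reactogenicity summaries. It would be wrong to infer that a conclusion about prolonged reactions turns on this, since no safety hypothesis is tested. Early stopping does not affect temperature, and the primary non-inferiority analysis and the sample size are unaffected.

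**What to change.** In Protocol 8.3.2, delete the ordering words and reconcile the sentence with footnote t. State that solicited symptoms are recorded daily for the full 7 days after each vaccination in all participants, and that any event ongoing at that point is recorded until it resolves. Use the same statement in the Synopsis, 4.1, 6.8, the Overview in Section 8, 8.3.1 and the opening text of 8.3.2, and check that the e-diary instructions match.

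The cost is a wording change and a few extra diary days for participants whose symptoms persist or resolve early. Footnote t already asks for the extra days for persistent symptoms.

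If data have been collected before the change, establish which rule the e-diary applied and say so beside the duration and incidence tables.
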